2.0 RATIONALE

2.1 RATIONALE FOR THE TRIAL AND SELECTED SUBJECT POPULATION

University of Cincinnati sees 300-350 new head and neck cancer patients each year. Our institution conducted a retrospective analysis and identified twenty-eight patients over a 1-year period that were initially treated with definitive concurrent CRT or RT alone who subsequently developed local recurrence and required salvage resection. Amongst the twenty-eight patients identified, seven patients developed a recurrence within 12 months and twelve patients died over the course of 2 year follow up which necessitates the need for additional active therapy. However, because these patients have already undergone multiple treatment modalities, it is important to study the efficacy and safety of this approach.

The known side effects of PD-1 inhibitors are unique from chemotherapy and radiation effects, and therefore we hypothesize that the addition of adjuvant Nivolumab to those patients who have undergone salvage resection is feasible and safe and will not result in excessive toxicity.

2.2 EFFICACY ENDPOINTS

Relapses are the most common cause of death in these patients. Therefore, our primary and secondary efficacy endpoints will be disease-free survival (DFS) at 2 and 1 years, respectively, which will reflect late and early relapse. DFS is defined as the duration from the time of treatment allocation to the time of discovery of the first evidence after treatment of any tumor (local, regional, metastatic, or second primary) or death from any cause.

2.3 SAFETY ENDPOINTS

Clinically, the addition of Nivolumab after salvage resection has not been explored. Nivolumab has already been approved in lung cancer, renal cell cancer and now head and neck cancer. Based on the current safety profile of Nivolumab alone we do not expect to observe any additional adverse effects and that this will therefore be a safe combination. Checkmate-141 reported a 13% Grade 3 and 4 adverse event rate¹ and we anticipate similar results from our trial.

2.4 BIOMARKER RESEARCH/ENDPOINTS RATIONALE

Multiple trials have demonstrated that PD-L1 expression on tumor can correlate with response but this does not appear to be a consistently predictive biomarker. The goal of this collateral study is to identify possible patterns in responders and non-responders. This will be done by (1) characterizing the type of tumor infiltrating lymphocytes (TIL) that are present at baseline (pre-drug) which include

CD4, CD8 and T reg cells as well as ratios (2) identifying an inflammatory gene signature from tumor tissue in patients that did not relapse versus those who did and (3) unique alterations of T cell phenotype and function pre-drug and after therapy.

3.0 ETHICAL CONSIDERATIONS

3.1 GOOD CLINICAL PRACTICE

This study will be conducted in accordance with Good Clinical Practice (GCP), as defined by the International Conference on Harmonization (ICH) and the United States Code of Federal Regulations, Title 21, Part 50 (21 CFR 50).

The study will be conducted in compliance with the protocol. The protocol and any amendments and the subject informed consent will receive Institutional Review Board (IRB) approval prior to initiation of the study.

3.2 INSTITUTIONAL REVIEW BOARD

Before study initiation, the investigator must have written and dated approval from the IRB for the protocol, consent form, subject recruitment materials (e.g., advertisements), and any other written information to be provided to subjects. The investigator should also provide the IRB with a copy of the Investigator Brochure or product labeling information to be provided to subjects and any updates.

The investigator should provide the IRB with reports, updates and other information (e.g., expedited safety reports, amendments, and administrative letters) according to regulatory requirements or institution procedures.

3.3 INFORMED CONSENT

Investigators or properly delegated study personnel must ensure that subjects are clearly and fully informed about the purpose, potential risks, and other critical issues regarding clinical studies in which they volunteer to participate.

In situations where consent cannot be given by subjects, their legally acceptable representatives must be clearly and fully informed about the purpose, potential risks, and other critical issues regarding clinical studies in which the subject will participate.

4.0 METHODOLOGY/INVESTIGATIONAL PLAN

4.1 DIAGNOSIS/CONDITION FOR ENTRY INTO THE TRIAL

Histologically or cytologically confirmed locally recurrent HNSCC including the oral cavity, larynx or pharynx (except nasopharynx).

4.2 SUBJECT INCLUSION CRITERIA

In order to be eligible for participation in this trial, the subject must:

1. Be willing and able to provide written informed consent for the trial.
2. Be ≥ 18 years of age on day of signing informed consent.

3. Patients must have had prior definitive therapy with radiation (with or without prior surgical resection and/or chemotherapy) who have underwent salvage resection and have no other curable options.
4. Patients must undergo salvage resection with curative intent.
5. Pre-operative scans including neck imaging preferably PET/CT and CT neck w/contrast. Chest imaging (which would be included in PET/CT) must also be completed but can be performed pre- or post-operatively as long as before trial treatment. CT chest and CT neck w/contrast or MRI neck and chest would also be acceptable.
6. Be able to provide archived biopsy or resected tissue.
7. Have a performance status of ≤ 2 on the ECOG Performance Scale.
8. Demonstrate adequate organ function as defined in Table 1.

Table 1. Adequate Organ Function Laboratory Values

System	Laboratory Value
Hematological	
Absolute neutrophil count (ANC)	$\geq 1,000$ /mcL
Platelets	$\geq 75,000$ / mcL
Hemoglobin	≥ 8 g/dL or ≥ 5.6 mmol/L without transfusion or EPO dependency (within 7 days of clinical assessment)
Renal	
Serum creatinine OR Measured or calculated ^a creatinine clearance (GFR can also be used in place of creatinine or CrCl)	Within upper limit of normal (ULN) OR ≥ 30 mL/min for subject with creatinine levels > institutional ULN
Hepatic	
Serum total bilirubin	$\leq 1.5 \times \text{ULN}$ OR Direct bilirubin $\leq \text{ULN}$ for subjects with total bilirubin levels > 1.5 ULN
AST (SGOT) and ALT (SGPT)	$\leq 2.5 \times \text{ULN}$
Albumin	≥ 2.5 mg/dL
Coagulation	
International Normalized Ratio (INR) or Prothrombin Time (PT)	$\leq 1.5 \times \text{ULN}$ unless subject is receiving anticoagulant therapy as long as PT or PTT is within therapeutic range of intended use of anticoagulants
Activated Partial Thromboplastin Time (aPTT)	$\leq 1.5 \times \text{ULN}$ unless subject is receiving anticoagulant therapy as long as PT or PTT is within therapeutic range of intended use of anticoagulants

^aCreatinine clearance should be calculated per institutional standard.

9. Female subject of childbearing potential should have a negative urine or serum pregnancy within 72 hours prior to receiving the first dose of study medication. If the urine test is positive or cannot be confirmed as negative, a serum pregnancy test will be required.
10. Female subjects of childbearing potential should be willing to use 2 methods of birth control or be surgically sterile, or abstain from heterosexual activity for the course of the study through 5 months after the last dose of study. Subjects of childbearing potential are those who have not been surgically sterilized or have not been free from menses for > 1 year.
11. Male subjects who are sexually active with women of childbearing potential should agree to use an adequate method of contraception starting with the first dose of study therapy through 7 months after the last dose of study therapy.

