1. **Objective:** Evaluate resected tumor specimens for CD4, CD8 and T reg ratios. The study will also determine PD-L1 expression on tumor and surrounding infiltrating cells along with KI-67 and granzyme expression in tumor tissue. This analysis will aim to provide a pre-PD1 inhibitor immunophenotype that can be assessed from tumor tissue to identify markers that determine relapse.
2. **Objective:** Study peripheral blood T cell response after anti-PD1 treatment by multi-

color flow cytometry to determine type of immune response on peripheral T cells.

3. **Objective:** Identify an inflammatory gene signature by RNA sequencing in tumor tissue that correlates with those who did not relapse versus those who did.

[figure not shown]
Study Design:

This study will be a 1-arm phase II trial including 39 patients with head and neck squamous cell carcinoma (HNSCC) eligible for salvage resection after definitive radiation +/- chemotherapy. Patients who undergo curative intent salvage resection will be screened and consented to receive Nivolumab following resection. Patients will receive Nivolumab every 4 weeks. Nivolumab will continue for 6 months (6 doses) as shown in schema.

For correlative studies, archived biopsy samples and/or resection tissue will be assessed by H&E and IHC for immune phenotype. Blood samples will also be collected for correlative studies.

Patients will be followed every 4 weeks during treatment, followed by a 30-day safety visit and then every 3 months thereafter for disease and survival status. Patients will be assessed for 1 and 2-year disease free survival (DFS) as well as for toxicity during treatment.

Trial Diagram:

Study Population:

For entry into the study, the following criteria MUST be met:

Key Inclusion Criteria:

- Histologically or cytologically confirmed head and neck squamous cell carcinoma (HNSCC).
- Prior definitive therapy with chemo-radiotherapy or radiation alone.
- Patients must have undergone salvage resection with curative intent.
- Adult subjects ≥ 18 years of age.
- Adequate bone marrow and organ function.
- ECOG Performance status ≤ 2 .
- Must be able to understand and sign written informed consent.

Key Exclusion Criteria:

- Patients who did not receive radiotherapy as prior definitive treatment.
- Patients who continue to have gross measurable residual disease after salvage surgery.
- Patients who underwent salvage surgery for palliative purposes i.e. for symptom control.

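### Two limits in eligibility Table 1 are wrong as written: the paired hemoglobin figures differ by about 1 g/dL, and the albumin limit in mg/dL excludes nobody

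*Combined protocol and SAP*

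**What the plan says.** Inclusion criterion 8 in Section 4.2 requires that the subject "Demonstrate adequate organ function as defined in Table 1". The laboratory values in that table are therefore conditions of entry.

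Two rows matter here:

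- **Hemoglobin:** at least 8 g/dL, or at least "5.6 mmol/L without transfusion or EPO dependency".
- **Albumin:** at least 2.5 mg/dL.

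No other place gives a number that settles either row. The key inclusion criteria in the Study Synopsis say only "Adequate bone marrow and organ function". Table 3 (Section 7.6.2) lists hemoglobin and albumin among the tests to be done, with no units or limits.

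**The concern.** A limit printed in two units should be one concentration written twice. The hemoglobin pair does not look like that: 5.6 mmol/L is higher than the usual conversion of 8 g/dL. The albumin limit has a different fault, because serum albumin is measured in grams per deciliter and a limit of a few milligrams per deciliter lies far below any value a patient could have.

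Both rows decide who may enter. The first dose is given 28 to 77 days after salvage surgery (Section 6.0), so the checks apply to recently operated patients. Treatment may start only after the coordinating-center investigator confirms eligibility, and that confirmation is made against Table 1. Someone who applies the albumin row literally must pass every value. Someone who silently reads another unit is enforcing a limit that the protocol does not state, and may log deviations with no basis in the text.

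**Working it through.** **Inputs from the documents (Section 4.2, Table 1):** hemoglobin 8 g/dL and 5.6 mmol/L; albumin 2.5 mg/dL.

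**Input assumed:** the molar mass of hemoglobin, which the documents do not give. Laboratories usually report mmol/L on the monomer basis, taken here as 16,114 g/mol, with 16,000 to 16,500 g/mol as the range. The tetramer, 64,458 g/mol, is tried as a variant.

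**Formula:** mmol/L = g/dL × 10 ÷ molar mass × 1,000. At 16,114 g/mol the factor is 10,000 ÷ 16,114 = 0.6206.

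**Step 1: the plan's implied equivalence.** For 8 g/dL to equal 5.6 mmol/L the factor would have to be 5.6 ÷ 8 = 0.70, a molar mass of 10,000 ÷ 0.70 = about 14,286 g/mol. That is well outside the assumed range, so the pair is not reproduced.

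**Step 2: convert each figure.**

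| Molar mass (g/mol) | Factor | 8 g/dL in mmol/L | 5.6 mmol/L in g/dL | Gap (g/dL) |
|---|---|---|---|---|
| 16,000 | 0.6250 | 5.00 | 8.96 | 0.96 |
| 16,114 | 0.6206 | 4.96 | 9.02 | 1.02 |
| 16,500 | 0.6061 | 4.85 | 9.24 | 1.24 |
| 64,458 (tetramer) | 0.1551 | 1.24 | 36.1 | 28.1 |

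The gap is about 1 g/dL on any monomer figure tried, which is too large for rounding. The tetramer basis pushes the two figures much further apart.

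**Step 3: what the row does.** Read literally, *or* admits a patient who meets either limit. The union of at least 8 g/dL and at least about 9.0 g/dL is at least 8 g/dL, so the lower figure governs. A patient between about 8.0 and 9.0 g/dL is turned away only if a site uses the mmol/L figure by itself.

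**Step 4: albumin.** This needs only 1 g = 1,000 mg.

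- 2.5 mg/dL ÷ 1,000 = 0.0025 g/dL.
- Take 1 to 2 g/dL as an assumed range for severe hypoalbuminemia. That is 1,000 to 2,000 mg/dL.
- 1,000 ÷ 2.5 = 400 and 2,000 ÷ 2.5 = 800.

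Even such patients pass the written limit 400- to 800-fold, so the numeric criterion excludes nobody. If g/dL was meant, the cell is off by a factor of 1,000.

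**The case against.** The case against accepts the arithmetic and disputes the consequences. Most of it stands.

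- **Hemoglobin.** A reader might infer that the table sets two competing rules, so that eligibility turns on the unit a laboratory reports. The text does not support that. With *or* between the figures, 8 g/dL governs and the mmol/L figure is redundant. The conflict needs a site that applies the mmol/L figure alone, and nothing in the documents points to one. Section 9.4 names two institutions, the study runs under a US IND, and the rest of the table uses conventional units. That both laboratories report in g/dL is nevertheless an assumption.
- **Albumin.** A reader might infer that patients with dangerously low albumin will be enrolled unchecked. That goes too far. A thousandfold slip in a routine unit is easy for a clinician to see. Exclusion criterion 12 in Section 4.3 lets the investigator exclude a patient for a laboratory abnormality, and Sections 5.6, 6.0, 7.4.4 and 7.7.1 require coordinating-center confirmation before treatment. These safeguards are real, but the first is discretionary, neither sets a number for albumin, and neither corrects the cell.
- **Inference.** Neither row enters the DFS definition, the 33% and 53% hypotheses, the stage boundaries or the sample size in Section 9.3.

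These points limit the practical effect. They do not make either cell right.

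**Conclusion.** The point holds as a correction of two cells in a binding table.

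The hemoglobin figures differ by about 1 g/dL (0.96 to 1.24 g/dL), given a monomer molar mass of 16,000 to 16,500 g/mol, which is an outside assumption. The albumin finding needs only the definition of a milligram: the written limit is 0.0025 g/dL and has no effect.

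The documents do not show which hemoglobin figure was intended, or that the albumin entry is anything more than an apparent unit slip. They also give no ground for claiming a demonstrated safety consequence or a material change in who is enrolled. The practical effect is probably small if sites report hemoglobin in g/dL and notice the albumin unit. Sample size, power and the primary analysis are untouched, so this is a minor correction.

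**What to change.** In the next amendment the sponsor should:

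1. State the intended hemoglobin limit and make the g/dL and mmol/L figures convert into each other.
2. Check and correct the albumin unit, and state the intended limit.

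No value is proposed here for either row, since these are the sponsor's clinical decisions. The cost is two table cells in Section 4.2, with no change to the statistical sections.

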4.3 SUBJECT EXCLUSION CRITERIA

The subject must be excluded from participating in the trial if the subject:

1. Did not receive at least radiotherapy as prior definitive treatment.
2. Has gross measurable residual disease after surgery or underwent surgery for palliative purposes i.e. for symptom control.
3. Has a diagnosis of immunodeficiency or is receiving systemic steroid therapy or any other form of immunosuppressive therapy within 7 days prior to the first dose of trial treatment. Short bursts of steroids of 5-7 days (for COPD exacerbation or other similar indication) are allowed.
4. Has nasopharyngeal or sinonasal carcinoma.
5. Has confirmed distant metastatic disease. Metastatic disease in neck lymph nodes is considered local disease.
6. Has a known history of active TB (Bacillus Tuberculosis).
7. Hypersensitivity to Nivolumab or any of its excipients.
8. Has a known additional malignancy that was diagnosed within the last three years that is either progressing or requires active treatment. Exceptions include basal cell carcinoma of the skin or squamous cell carcinoma of the skin that has undergone potentially curative therapy or in situ cervical cancer.
9. Has active autoimmune disease that has required systemic treatment in the past 2 years (i.e. with use of disease modifying agents, corticosteroids or immunosuppressive drugs). Replacement therapy (e.g., thyroxine, insulin, or physiologic corticosteroid replacement therapy for adrenal or pituitary insufficiency, etc.) is not considered a form of systemic treatment.
10. Has known history of, or any evidence of active, non-infectious pneumonitis.

11. Has an active serious infection requiring systemic (IV) therapy.
12. Has a history or current evidence of any condition, therapy, or laboratory abnormality that might confound the results of the trial, interfere with the subject's participation for the full duration of the trial, or is not in the best interest of the subject to participate, in the opinion of the treating investigator.
13. Has known psychiatric or substance abuse disorders that would interfere with cooperation with the requirements of the trial.
14. Is pregnant or breastfeeding, or expecting to conceive or father children within the projected duration of the trial, starting with the pre-screening or screening visit through 120 days after the last dose of trial treatment.
15. Has a known history of Human Immunodeficiency Virus (HIV) (HIV 1/2 antibodies).
16. Has known active Hepatitis B (e.g., HBsAg reactive) or Hepatitis C (e.g., HCV RNA [qualitative] is detected).
17. Has received a live vaccine within 30 days of planned start of study therapy.

Note: Seasonal influenza vaccines for injection are generally inactivated flu vaccines and are allowed; however intranasal influenza vaccines (e.g., Flu-Mist®) are live attenuated vaccines, and are not allowed.

18. Has a history of (non-infectious) pneumonitis that required steroids or current pneumonitis.

4.4 WOMEN OF CHILDBEARING POTENTIAL

A woman of childbearing potential (WOCBP) is defined as any female who has experienced menarche and who has not undergone surgical sterilization (hysterectomy or bilateral oophorectomy) and is not postmenopausal. Menopause is defined as 12 months of amenorrhea in a woman over the age of 45 years in the absence of other biological or physiological causes.

4.4.1 HIGHLY EFFECTIVE METHODS OF CONTRACEPTION

- Male condoms with spermicide
- Hormonal methods of contraception including combined oral contraceptive pills, vaginal ring, injectables, implants, and intrauterine devices (IUDs) such as Mirena® by WOCBP subject or male subject's WOCBP partner.
- Nonhormonal IUDs, such as ParaGard®
- Tubal ligation
- Vasectomy
- Complete Abstinence. *

*Complete abstinence is defined as complete avoidance of heterosexual intercourse and is an acceptable form of contraception for all study drugs. Subjects who choose complete abstinence are not required to use a second method of contraception, but female subjects must continue to have pregnancy tests. Acceptable alternate methods of highly effective contraception must be discussed in the event that the subject chooses to forego complete abstinence.

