5.7 USE IN PREGNANCY

If, following initiation of the study drug, it is subsequently discovered that a study subject is pregnant or may have been pregnant at the time of study exposure, including during at least 5 half-lives after product administration, the investigator must immediately notify the University of Cincinnati PI and BMS of this event and complete and forward a Pregnancy Surveillance Form to BMS within 24 hours and in accordance with SAE reporting procedures described in Section 8.

In most cases, the study drug will be permanently discontinued in an appropriate manner (e.g., dose tapering if necessary for subject safety).

In the rare event that the benefit of continuing study drug is thought to outweigh the risk, after consultation with BMS and the University of Cincinnati PI, the pregnant subject may continue study drug, after a thorough discussion of benefits and risk with the subject.

Protocol required procedures for study discontinuation and follow-up must be performed on the subject unless contraindicated by pregnancy (e.g., x-ray studies). Other appropriate pregnancy follow-up procedures should be considered if indicated.

Follow-up information regarding the course of the pregnancy, including perinatal and neonatal outcome and where applicable, offspring information must be reported on the Pregnancy Surveillance form.

Any pregnancy that occurs in a female partner of a male study participant should be reported to BMS and the University of Cincinnati PI. Information on this pregnancy will be collected on the Pregnancy Surveillance Form.

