6.0 STUDY FLOW CHART

Trial Period	Screening	Treatment							Post-Treatment/Follow-up ^q
		1	2	3	4	5	6		
Scheduling Window (Days)	-28 to -1	0 ^(j)	± 3	± 3	± 3	± 3	± 3	30 Days post-discon +/- 3 ^(l)	Every 12 weeks +/- 4 weeks
Adjuvant Treatment (Week)		1	5	9	13	17	21		
Informed Consent	X								
Inclusion/ Exclusion Criteria ^(R)	X								
Demographics and Medical History ^(m)	X								
Prior and Concomitant Medication Review	X	X	X	X	X	X	X	X	
Nivolumab Administration ^(a)		X	X	X	X	X	X		
Post-study anticancer therapy status								X	
Survival and Disease Status ^(k)									X
Review Adverse Events		X	X	X	X	X	X	X ⁽ⁱ⁾	
Full Physical Examination	X							X	
Directed Physical Examination		X	X	X	X	X	X		X ^(c)
Vital Signs and Weight	X ⁽ⁿ⁾	X	X	X	X	X	X	X	

Trial Period	Screening	Treatment							Post-Treatment/Follow-up ^q
		1	2	3	4	5	6		
Scheduling Window (Days)	-28 to -1	0 ^(j)	± 3	± 3	± 3	± 3	± 3	30 Days post-discon +/- 3 ^(l)	Every 12 weeks +/- 4 weeks
Adjuvant Treatment (Week)		1	5	9	13	17	21		
ECOG Performance Status ^(b)	X		X	X	X	X	X		
Pregnancy Test – Urine or Serum -HCG	X ^(p)								
CBC with Differential	X ^(o)	X ^(o)	X	X	X	X	X	X	
Comprehensive Serum Chemistry Panel ^(d)	X ^(o)	X ^(o)	X	X	X	X	X	X	
Urinalysis	X ^(o)	X ^(o)			X			X	
T3, FT4 and TSH	X ^(o)	X ^(o)			X			X	X ^(h)
PT/INR, PTT	X ^(o)								
Tumor Imaging ^(e)	X								X ^(e)
Archival Tissue Collection ^(f)	X							X ^(f)	
Correlative Studies Blood Collection ^(g)		X	X					X ^(g)	

a) Nivolumab will start 28-77 days after surgery. Start of cycle on Day 1 +/- 3 days.

b) ECOG to be done prior to treatment administration. For Day 1, must be done within 10 days but does not need to be repeated for Day 1 only.

c) Only required if assessing for disease recurrence.

- d) Magnesium, Phosphorous, LDH, uric acid should also be checked as part of CMP labs.
- e) PET/CT and CT neck with contrast preferred for screening. CT neck with contrast and CT chest or MRI neck and chest is also acceptable. Neck imaging must be completed pre-operatively but chest imaging may be pre or post-operatively. Follow-up tumor imaging will be at discretion of treating physician but is not required per protocol.
- f) Archival Resected tissue will be collected from pathology and sectioned per procedure manual. If biopsy or resection is performed per SOC at recurrence, tissue will also be collected at that time for analysis.

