- g) On Day 1 and week 5, ensure correlative samples are collected prior to protocol treatment. A 3rd sample should be collected at the end of treatment visit. Correlatives will be placed in four 10ml lavender EDTA tubes.
- h) Thyroid function labs can be checked at physician's discretion on post treatment follow up.
- i) SAEs should be evaluated out to 100 days after drug discontinuation. All AEs should be followed until \leq Grade 1 or new therapy has begun. All non-serious AEs must be followed continuously for at least 30 days.
- j) Adjuvant treatment must be started 28-77 days after salvage surgery.
- k) May be assessed by phone or clinic visit
- l) Post discontinuation visit should occur at 30 days +/-3 days as above, or before new therapy begins, whichever occurs first.
- m) Medical History from last 10 years should be included
- n) Height also required only at screening
- o) Labs must be collected within 10 days of first treatment and within 72 hours prior to subsequent treatments. Screening labs can be used for Day 1 as long as within window.
- p) Must be collected within 72 hours of Day 1.
- q) Subjects who discontinue for reasons other than progressive disease will have post-treatment follow-up for disease status until disease progression, initiating a non-study cancer treatment, withdrawing consent or becoming lost to follow-up or the end of the study whichever occurs first. After documented disease progression each subject will be followed by telephone for overall survival until death, withdrawal of consent, or the end of the study, whichever occurs first.
- r) Protocol treatment must begin only after eligibility criteria are confirmed by the UC PI (registration)

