8.3 PREGNANCY AND LACTATION

If, following initiation of the investigational product, it is subsequently discovered that a study participant is pregnant or may have been pregnant at the time of investigational product exposure, including during at least 5 half-lives after product administration, the investigational product will be permanently discontinued in an appropriate manner (e.g., dose tapering if necessary for participant).

The investigator must immediately notify the University of Cincinnati PI and BMS at [contact] of this event via the Pregnancy Surveillance Form in accordance with SAE reporting procedures.

Protocol-required procedures for study discontinuation and follow-up must be performed on the participant.

Follow-up information regarding the course of the pregnancy, including perinatal and neonatal outcome and, where applicable, offspring information must be reported on the Pregnancy Surveillance Form [provided upon request from BMS].

Any pregnancy that occurs in a female partner of a male study participant should be reported to BMS and the University of Cincinnati PI. Information on this pregnancy will be collected on the Pregnancy Surveillance Form. In order to collect any pregnancy surveillance information from the female partner, the female partner must sign an informed consent form for disclosure of this information. Such events must be reported within 24 hours to the University of Cincinnati PI and within 24 hours to BMS Global Pharmacovigilance (Attn: [contact] [contact])

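### The abstinence note in 4.4.1 calls for continued pregnancy tests, but the only scheduled test precedes dose 1, leaving doses 2 to 6 without one

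*Combined protocol and SAP*

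**What the plan says.** Section 4.4.1 lets a subject who chooses complete abstinence go without a second contraceptive method, "but female subjects must continue to have pregnancy tests". It states no interval and no visits.

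The timing of the test is set in four places:

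- **Inclusion criterion 9 (4.2):** a negative urine or serum result in the 72 hours before the first dose.
- **Flow chart (6.0):** the row "Pregnancy Test – Urine or Serum -HCG" is marked once, in the screening column. The cells for treatment weeks 1, 5, 9, 13, 17 and 21, the 30-day visit and follow-up are empty.
- **Footnote p (6.0):** "Must be collected within 72 hours of Day 1".
- **Section 7.7.1:** a serum test in the 72 hours before the first dose, with urine as the fallback.

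Section 7.7.2, on the treatment period, only refers back to the flow chart. The laboratory table in 7.6 says who is tested, not when.

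Section 4.4.2 bars pregnancy during treatment and for up to 5 months after the last dose. Section 5.7 applies when "it is subsequently discovered that a study subject is pregnant". It then says "In most cases, the study drug will be permanently discontinued in an appropriate manner", but allows that in rare cases, after consultation, "the pregnant subject may continue study drug, after a thorough discussion of benefits and risk with the subject". Section 8.3 has the same trigger but no exception: "the investigational product will be permanently discontinued in an appropriate manner".

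**The concern.** The word for continuing and the plural for tests are most naturally read as repeat testing during treatment, which the schedule does not provide. A site that takes the note literally must invent an interval; a site that follows the flow chart tests once and then gives five more doses. With two institutions enrolling, practice could differ between them.

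What is at stake is fetal exposure. The protocol's response to a pregnancy depends on finding it, and no scheduled step would find an early, unsuspected pregnancy before doses 2 to 6. The efficacy endpoint, the sample size and the primary analysis are not affected.

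**Working it through.** The plan gives no figure to reproduce. The check is a count of scheduled tests against scheduled doses, followed by the interval between them.

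**Inputs**

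- Doses: six, at weeks 1, 5, 9, 13, 17 and 21 (5.6, Table 2; 6.0).
- Scheduled pregnancy tests: one, 0 to 3 days before Day 1 (criterion 9; footnote p; 7.7.1).
- Blood count and the "Comprehensive Serum Chemistry Panel": marked at every dosing visit (6.0). Footnote o sets a 72-hour window before later doses. It is attached to the laboratory rows but not to the pregnancy-test row.
- Urinalysis: marked at screening, weeks 1 and 13, and the 30-day visit (6.0).
- Number of women of childbearing potential: not given. Assumed range: 0 to 4 of 39.

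**Coverage**

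- Doses with a scheduled test: 1 of 6.
- Doses without: 6 − 1 = 5 (weeks 5, 9, 13, 17 and 21).

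**Interval from the only test to the last dose**

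- Week 21 − week 1 = 20 weeks = 20 × 7 = 140 days.
- Adding the 0 to 3 days by which the test precedes Day 1 gives 140 to 143 days on the planned schedule.
- With dose 1 fixed and dose 6 moved within its ±3-day window: 140 − 3 = 137 to 143 + 3 = 146 days. Dose delays permitted under 5.6.5.3 and 5.6.5.4 lengthen it further.
- With a test in the 72 hours before each dose, the interval before any dose is at most 3 days.

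**Added tests**

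- Per woman: 5 (weeks 5, 9, 13, 17 and 21), or 6 with an optional test at the 30-day visit.
- Whole trial, 0 to 4 women: 5 × 0 = 0 to 5 × 4 = 20; with the optional test, 6 × 0 = 0 to 6 × 4 = 24.
- If urine is used, urinalysis already falls at 1 of the 5 added dosing visits (week 13), so a separate sample is needed at 5 − 1 = 4 visits.

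**Could another provision supply the missing tests?** Inclusion criterion 10 requires two methods, sterility or abstinence, which lowers the risk but does not detect failure. Adverse event review and a directed examination take place at each dosing visit, but neither calls for an hCG test. Section 7.1 permits unscheduled procedures when the investigator judges them clinically necessary, and an unsuspected pregnancy would not prompt that judgement. None of these schedules a repeat test.

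**The case against.** The strongest reply is that the sentence only marks the limit of what abstinence waives: the second method goes, and whatever testing is scheduled stays. On that reading nothing conflicts, because all the timed provisions agree on one test before dose 1. The note also reads as generic text, since it speaks of study drugs in the plural in a single-drug trial. It covers only subjects who choose abstinence, whereas the proposed change covers all women of childbearing potential. Exclusion criterion 14 also keeps out anyone expecting to conceive through 120 days after the last dose. Finally, criterion 9 and the flow chart accept urine or serum equally, so serum is the default only in 7.7.1.

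Part of this stands. The milder reading is possible, no provision states a 4-weekly frequency, and the safeguards lower the risk. The saving of a new draw holds only if serum is used.

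The gap remains all the same. A single test before treatment is hard to continue. If the note means that abstinent women are not exempt from continuing tests, it presupposes that other women of childbearing potential have them too, so the wider scope follows. Contraception and the exclusion criteria detect nothing. On either reading, five doses have no scheduled test.

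**Conclusion.** The concern holds. The note implies ongoing testing, the schedule provides one test, and doses 2 to 6 have none. The size is 5 of 6 doses uncovered and 140 to 143 days from the only test to dose 6 on the planned schedule.

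The conclusion that doses lack a scheduled test rests on the documents alone. That the note intends repeat testing rests on the more natural of two readings. The number of women affected is unknown, and 0 to 4 of 39 is an assumption; at the lower end nobody is exposed. This is a patient-safety correction that should be made, not a flaw in the statistical design.

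**What to change.** For women of childbearing potential only:

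1. Mark the pregnancy-test row in the section 6.0 flow chart before dosing at weeks 5, 9, 13, 17 and 21. A test at the 30-day visit is optional.
2. Extend footnote p so that the test falls within 72 hours before each dose, not only the first.
3. Use serum from the blood already drawn at those visits, within the 72-hour window that footnote o sets.
4. Have the 4.4.1 note refer to the tests listed in section 6.0.

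Rewording the note alone would remove the ambiguity but leave five doses without a scheduled test.

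The textual cost is one row, one footnote and one cross-reference. The operational cost is the 5 inexpensive tests per woman counted above (6 with the optional one), with no new visit and, if serum is used, no new draw. If no such woman enrolls, the cost is the text edit.
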